## 7.1.CENTRAL SPECIMEN REPOSITORY

The National Institute for Research in Tuberculosis (NIRT) in Chennai will be the Central Repository for the India RePORT sites acting under contract to the DBT. NIRT will provide centralized training and laboratory support to the CRUs as needed.

### Specimens for Long Term Storage at the Central Repository

All processing and aliquoting of samples will take place in the CRU laboratory prior to sending samples to the Central Repository (Table 4). Samples will then be shipped to the Central Repository where they will be curated, managed, and stored for a maximum of 10 years. Samples will only be destroyed with written permission of the sponsor and according to local regulatory guidelines.

The sites will be provided with sample collection kits. Details for the collection, processing, storage, and shipping of samples collected as part of the Common Protocol are presented in the RePORT-India Consortium Manual of Operation (MOP).

**TABLE 4: BIOSTORAGE STUDY SPECIMEN COLLECTION AND STORAGE CHART (ADULTS AND CHILDREN)**

Specimens Type	Adults and Children ( years)	Children (< 5 years) a
Whole blood (PAXgene tubes)	2.5 mL	2.5 mL b
Whole blood (QuantIFERON-Gold InTube)	3.0 mL (1.0 mL/tube)	3.0 mL (1.0 mL/tube)
Whole blood (Genotyping)	10 mL	DO NOT COLLECT IF VOLUME EXCEEDS REGULATORY LIMITS
PBMCs	8.0 mL (BD CPT™)	4.0 mL (BD CPT™)
Plasma	Harvested from BD CPT™ (PBMC) tubes above	Harvested from BD CPT™ (PBMC) tubes above
Urine	Spot urine (10 mL)	Spot urine (10 mL)
Sputum	Whatever volume is possible to collect	Whatever volume is possible to collect
Extracted host RNA	Prepared from PAXgene tube	Prepared from PAXgene tube
M.Tb isolate	Cohort A	Subculture of original Mtb isolate and relapse or failure isolate.
	Cohort B	Subculture of confirmatory Mtb isolate from each subject who develops active TB

a Refer to weight chart for maximum blood volume collection limits in MOP. Indicated blood collection volumes are intended for children ≥ 5 kg (or 11 lbs) .

bExclude from collection if combined study and biobank blood volume limit is exceeded –Maximum combined blood volume collection is limited 2.5 mL/kg.

## 8. ASSESSMENT OF OUTCOME

*Aim 1: To examine the host and microbial factors associated with TB treatment outcomes*

- Primary outcome for Aim 1 will be a composite poor treatment outcome, defined as treatment failure, recurrence or death within 24 months of TB treatment initiation.
- Secondary outcomes will include time-to-sputum AFB negativity, time-to-culture negativity, and time-to-detection of MTB using liquid sputum culture on mycobacteria growth indicator tubes (MGIT).

*Aim 2: To investigate the host and microbial factors associated with the progression from infection to active TB disease*

- Primary outcome is incident TB within 24 months (best outcome to assess what factors are associated with the risk of progressing to active TB)
- Secondary outcome will be proportion with co-prevalent TB at time of initial household screening.

*Aim 3: To explore the host and microbial factors associated with MTB transmission*

- Primary outcome will be incident infection defined as conversion of TST or QGIT or at entry a positive TST (> 15mm) or QGIT in a child <5 years.
- Secondary outcome will be prevalent active TB at entry or incident TB among HH contacts that have the same DNA fingerprint using MIRU based genotyping at NIRT.

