**TABLE 1. C-TRIUMPH – STUDY OBJECTIVES AND TIMEFRAME**

KEY OVERARCHING SCIENTIFIC QUESTIONS				
HOST FACTORS		MICROBIAL FACTORS		
Which host factors, individually or combined, are associated with TB treatment outcomes, disease progression and transmission in India?		Which microbial factors, individually or combined, are associated with TB treatment outcomes, disease progression and transmission in India?		
SCIENTIFIC HYPOTHESES				
H0 Potentially modifiable (HIV, DM, tobacco, IAP, alcohol, undernutrition) and non-modifiable host factors (age, sex, genetics) alone or in combination have the greatest association with TB treatment outcome, disease progression and transmission in India		H0 Specific Mtb strain lineages and drug susceptibility patterns are most highly associated with TB treatment outcome, disease progression and transmission in India		
PRIORITY RESEARCH STUDIES				
Clinical/Epi Studies		Lab Studies	Clinical/Epi Studies	Lab Studies
Specific Aim 1 Treatment Outcome	1. Prevalence and relative contributions of HIV, DM, tobacco, IAP and other modifiable risk factors on TB treatment outcome (Year 2-4) 2. Population PK of first line TB drugs, factors associated with their concentrations (NAT2, SLCO1B1 genotype, BMI, DM, HIV, etc), and treatment outcome (Year 3,4) 3. Hair samples to measure PK of first line TB drugs and correlate with drug adherence and plasma drug concentrations (Year 2-4)	1. Functional genetic variants in Indian populations within LTA4H and other components of eicosanoid and TNF pathways and associations with treatment outcomes (Years 4,5) 2. Whole blood transcriptome, proteosome, clinical presentation (Year 3) and treatment outcome (Year4) 3. Differential expression of PGLYR and NOD proteins in active TB (Year 3)	1 Mtb strain lineage, drug susceptibility, clinical presentation (Year 3) and treatment outcome (Year 5)	1. Transcriptome and lipid profile of serial Mtb strains from patients on treatment (Years 3,4) 2. Whole genome sequencing to assess microbial genes associated with PTB vs CNS TB in adults and children (Years 4,5)

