**HOUSEHOLD CONTACTS COHORT (ALL MUST APPLY)**

- i. All adults and children living in the same house as the adult (>18yrs) active Pulmonary TB participant during the 3 months prior to diagnosis of TB.
- ii. Ability of participant/legal guardian to provide informed consent/assent

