**F=Facilities-based activity; (F)= Facility Based activity only if indicated; H= Home-based activity; M=months**

 Any person who has active TB (prevalent or incident) is eligible for the Active TB Cohort if he or she consents. Active TB assessment will otherwise be done as included in this SOE if the participant does not enroll in the Active Cohort.

 All symptomatic household contacts will be referred immediately to the clinical facility for further evaluation. IPT will be recommended for all asymptomatic children under age 6 and all asymptomatic HIV+ household contacts

 Household food insecurity and dietary questionnaire

 Height, mid upper arm circumference, weight at baseline; at post entry visits, weight will be measured

 TST and QGIT will only be done if prior was negative

 HIV testing will only be done on adults. If there is a HIV+ adult in the household, then the legal guardian of the child will be asked if they want their child to be HIV tested

 Host mRNA, PBMC, saliva, will be performed on all at baseline and then a random subset of 200 households (n=800 contacts)

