## **8.2. OUTCOME MEASURES FOR HH CONTACT COHORT (COHORT B)**

**Active TB** is the primary outcome measure of interest in this cohort and will be defined as the following:

- a. No TB: Participant had no indication of MTB (pulmonary or extra-pulmonary) over follow up period
- b. Definite case: Culture-confirmed TB from any anatomic site.
- c. Probable case: Adult ( $\geq$  age 14) with symptoms of TB plus acid-fast bacilli seen on microscopic examination of sputum or biopsy specimen, but without culture-confirmation.
- d. Probable case: Child (<14) defined as:
  - i. Symptoms consistent with TB, specifically fever or cough for 2 weeks, or loss of weight or failure to gain weight normally, plus a history of contact with a suspected or confirmed case of active TB AND
  - ii. Acid-fast bacilli seen on microscopic examination of sputum or biopsy specimen  
OR  
Culture-negative after 2 attempts at sputum collection, using sputum induction, nasopharyngeal aspirates or gastric aspirates and have chest radiography that is consistent with intra-thoracic disease due to Mycobacterium tuberculosis.
  - iii. AND there is at least 1 of the following:
    - 1. A positive clinical response to standard multidrug anti-tuberculosis treatment OR
    - 2. Documented exposure to a case of active TB.
  - iv. AND immunological evidence of M. tuberculosis infection (e.g, reactive TST or positive IGRA)
- e. Possible case: Adult or child diagnosed with extra-pulmonary TB based on radiographic or other evidence, but without culture-confirmation.

**Incident MTB infection** is the secondary outcome measure in this cohort and will be defined as a positive TST or QGIT in children < 5 years or seroconversion of TST or QGIT among HH contacts during follow up.

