The primary outcome is diagnosis of active TB among individual HH contacts within 24 months of follow-up. Index PTB cases from the Active TB Cohort will form clusters and individuals within the HH of the index case are correlated. The association between host and microbial factors with progression from infection to active TB disease will be estimated using random effects.

Poisson regression models with index PTB cases as random effects. Random effects models will address the correlation of individuals within the HH. Relative risk ratios and 95% confidence intervals for host and microbial factors will be estimated from the models and will have a cluster-specific interpretation.

**Aim 2 Power.** We expect approximately 3200 HH contacts will be followed for an average duration of 2 years. We anticipate 85% (n=2720) of them will be HH contacts of a smear positive PTB case, 15% (n=480) will be contacts of a smear negative PTB. We estimate that at least 40% (n=1280) will be latently infected. We estimate that 320 (25%) of them would be recently infected and have a 15% 2 year risk of developing active TB. This would result in 48 active TB cases. We expect a background rate of active TB (regardless of latent TB infection) 0.37% per year, yielding an additional 24 cases. This yields an estimated 72 incident active TB cases.

**Aim 3.** The analysis set will be HH members of index PTB cases.

Primary outcome will be incident infection will be defined as positive TST or QGIT in children < 5 years or seroconversion of TST or QGIT among HH contacts. Secondary outcome will be prevalent or active TB with same MTB MIRU genotype.

Within household transmission rates will be calculated. Risk factor and covariate information collected on HH contacts will be used in the analysis. In addition the analysis will be adjusted for independent variables measured at HH level. A multivariate random effects Poisson regression model will be used to estimate the adjusted relative risk of MTB transmission to HH contacts in presence of host and microbial factors. The model will be adjusted for enrollment site (NIRT & BJMC).

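### Aim 3's primary outcome counts a positive test at entry as an event only in children under 5, so its age effect on transmission is partly produced by the definition

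*Protocol*

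**What the plan says.** The outcome is stated three times in the protocol.

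- Section 8, Aim 3 primary outcome: "incident infection defined as conversion of TST or QGIT or at entry a positive TST (> 15mm) or QGIT in a child <5 years".
- Section 9.1, Aim 3: "incident infection will be defined as positive TST or QGIT in children < 5 years or seroconversion of TST or QGIT among HH contacts".
- Section 8.2, as the secondary measure for the household contact cohort: "positive TST or QGIT in children < 5 years or seroconversion of TST or QGIT among HH contacts during follow up".

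The population is not limited by age or by entry test result. Section 9.1 says "The analysis set will be HH members of index PTB cases", and Section 5.2 admits "All adults and children living in the same house as the adult (>18yrs) active Pulmonary TB participant". The model is a multivariate random-effects Poisson regression, adjusted for site, that estimates an adjusted relative risk of transmission.

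On retesting, a footnote to the contact cohort schedule (Table 2 in Section 6) says "TST and QGIT will only be done if prior was negative".

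Age is one of the factors under study. The host-factor hypothesis in the objectives table of Section 3 states that modifiable and "non-modifiable host factors (age, sex, genetics) alone or in combination have the greatest association with TB treatment outcome, disease progression and transmission in India".

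**The concern.** The single outcome measures different things on either side of the fifth birthday. Under 5 it is infection already present at entry plus later conversion. At 5 and over it is later conversion only. An older contact who is positive on both tests at entry is not retested and can never be an event, while a child under 5 with the same results already is one.

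Because age is a hypothesised factor, the outcome depends by definition on something the study sets out to estimate. A raised relative risk in young children could be read as greater susceptibility when it only reflects the rule. Exposures found mainly in adults, such as tobacco, alcohol and diabetes, would look less harmful than they are in any analysis that leaves age out.

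**Working it through.** The protocol gives no power, event count or effect size for Aim 3, so there is no stated figure to reproduce. The check asks what the definition yields when age has no effect on conversion.

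**Inputs from the protocol (Section 9.1):** 3200 household contacts; at least 40% latently infected, over all ages.

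**Assumptions (not in the protocol):** p, the share of under-5s positive at entry, 10-30%; c, conversion over follow-up among entry-negatives, 10-25% and equal at every age.

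**Step 1, event probabilities.**
- Under 5: p + (1 − p)c.
- 5 and over, entry-positives removed as not at risk: c.
- 5 and over, entry-positives kept in the denominator, with q the share positive: (1 − q)c.

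**Step 2, direction.** The under-5 probability minus c is p + (1 − p)c − c = p(1 − c). This is above zero whenever some under-5s are positive at entry and conversion is below 100%. The relative risk therefore exceeds 1 under equal conversion, whatever the exact inputs. Keeping older entry-positives lowers the comparator and widens the gap.

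**Step 3, size.** The last column uses q = 40%, so the older event share is 0.6c.

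| c | p | Under-5 event share | RR, older entry-positives removed | RR, older entry-positives kept |
|---|---|---|---|---|
| 10% | 10% | 19.0% | 1.90 | 0.190/0.060 = 3.17 |
| 10% | 30% | 37.0% | 3.70 | 0.370/0.060 = 6.17 |
| 15% | 10% | 23.5% | 1.57 | 0.235/0.090 = 2.61 |
| 15% | 30% | 40.5% | 2.70 | 0.405/0.090 = 4.50 |
| 25% | 10% | 32.5% | 1.30 | 0.325/0.150 = 2.17 |
| 25% | 30% | 47.5% | 1.90 | 0.475/0.150 = 3.17 |

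If the protocol's 40% is applied at every age with c = 10%, the shares are 0.40 + 0.60 × 0.10 = 46% under 5, against 6% (RR 7.7, kept) or 10% (RR 4.6, removed). Over p = 10-40% and c = 5-30%, with equal positivity at all ages, the relative risk runs from 1.2 to 14.3.

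**Step 4, weight in the outcome.** Assume 10% of contacts (320) are under 5 and 40% of older contacts are positive at entry. With p = 10% and c = 20%, entry-positive children are 32 of 32 + 57.6 + 345.6 = 435.2 events, or 7%. With p = 40% and c = 10%, they are 128 of 128 + 19.2 + 172.8 = 320 events, or 40%.

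**Step 5, adjustment.** An under-5 term in the model takes up the definitional gap. That protects the other coefficients from confounding by the rule, but the age coefficient then is the gap plus any true effect, and the combined outcome cannot separate them.

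**Step 6, one rule for all ages.** Using conversion among entry-negatives only, the age ratio in the same scenario is c/c = 1.00.

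**Wording.** The 15 mm cut-off and the restriction to entry appear only in Section 8. In Section 8.2 the closing reference to follow-up could be read as covering the under-5 clause too. On that reading the clause would add little, because a child negative at entry who later tests positive is already a conversion, so entry positivity is the natural meaning. The text should say so.

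**The case against.** The under-5 clause has a sound purpose. Aim 3 concerns household transmission. Contacts enter two weeks to two months after the index case (Section 6.1), and household exposure covers the three months before diagnosis (Section 5.2), so infection passed on before entry belongs to the question. In a young child a positive test plausibly marks recent infection; in an adult it does not, given the expected 40% latent infection. The Aim 3 secondary outcome also counts disease already present at entry. All of this stands, and it is why the clause should be kept as a marker and not dropped.

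A reader might infer more than the protocol supports in four respects.

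- *No rate can be formed for an entry-positive child.* The person-years offset is stated for Aim 1 only. For Aim 3, Section 9.1 speaks of relative risk, and a Poisson model of a yes/no outcome can estimate that without person-time. Section 9.1 also mentions transmission rates but gives no denominator.
- *Every factor linked to young children is biased.* That follows only if the model omits age. Section 9.1 does not name age as a covariate, but it describes a multivariate model, and a full covariate list is commonly left to the SAP, which is not at hand.
- *Age is the main Aim 3 contrast.* Age is one of several factors in a hypothesis that spans all three aims. The Aim 3 epidemiological studies listed in Section 3 concern household dynamics and modifiable factors.
- *The sections give rival TST cut-offs.* Sections 8.2 and 9.1 give no competing number. The repetition is incomplete, not contradictory.

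The age coefficient itself remains. A SAP could analyse the components apart, but the pooled definition is fixed in the protocol.

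**Conclusion.** The point holds for the age estimate. As defined, the Aim 3 primary outcome gives an under-5 versus older relative risk above 1 with no true age effect, and age adjustment cannot correct that coefficient. Bias in other age-related factors is conditional on age being left out.

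The direction follows from the definition; the size does not. The range of about 1.3-3.7, or 2.2-6.2 with older entry-positives kept at 40%, rests on assumed entry positivity and conversion by age, for which the protocol gives only an overall 40% latently infected. It should not be quoted as the expected bias.

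This should be fixed, but it does not undermine the study: Aim 3 is exploratory, carries no power claim, and the data needed for a clean analysis are already scheduled.

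**What to change.** 1. Keep under-5 entry positivity as a marker of recent household transmission, but analyse it as a prevalence outcome in its own model.
2. Analyse post-entry conversion among entry-negative contacts of all ages as the other component, and take any age effect from it alone.
3. If the combined outcome is also reported, adjust it for age group (under 5 versus 5 and over), say whether older entry-positives are in the denominator, and draw no age contrast across 5 years from it.
4. State the TST cut-off and the restriction to entry identically in Sections 8, 8.2 and 9.1.

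The cost is wording in three places and one extra model, with no new data collection. The downside is fewer events per component, hence wider intervals. Making conversion the sole primary outcome would also remove the built-in age effect, but it would drop transmission before enrolment from the primary analysis, so it is a debatable trade-off and not needed here.

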### 8.1. OUTCOME MEASURES FOR ACTIVE TB COHORT (COHORT A)

Participants' samples from Cohort A will be saved in the bio-repository as they are likely to yield valuable information regarding biomarkers that correlate with changes over time with treatment, presence of clinical markers of disease severity (e.g., cavitory lesions on chest radiograph), and final outcome. Participants with relapsed or failed TB will be of special interest, reflecting a poor treatment outcome. All participants will be categorized by disease outcome status and by treatment completion status.

#### **Bacteriologic outcomes, drug-susceptible (DS) TB:**

1. **DS bacteriologic cure:** By the end of the RNTCP-specified standard, first-line multi-drug TB therapy, the participant has two or more consecutive respiratory secretion cultures negative for *M. tuberculosis*, and no evidence of bacteriologic failure.
2. **DS bacteriologic status indeterminate:** By the end of RNTCP-specified standard, first-line multi-drug TB therapy, the participant has resolution of symptoms of tuberculosis, but has not had two or more consecutive respiratory secretion cultures performed to establish cure status.

3. **Bacteriologic failure:** By the end of RNTCP-specified standard, first-line multi-drug TB therapy, the participant has one or more specimens from the respiratory tract or extra-pulmonary site that are culture-positive for *M. tuberculosis* in either liquid or solid media (with any colony count), when the culture has not been determined to be a false-positive culture.

**DS bacteriologic recurrence** Among participants who did not experience a clinical (as described below) or bacteriologic failure of therapy, the participant has a clinical specimen collected from any site during the follow-up phase that is culture-positive for *M. tuberculosis* in either liquid or solid media (with any colony count), when the culture has not been determined to be a false-positive culture.

**Clinical outcomes:** Participants who do not meet bacteriologic criteria to establish their final status may be assigned a clinical outcome.

1. **Clinical response:** A participant who has resolution, by the end of therapy, of symptoms attributable to tuberculosis.
2. **Clinical failure:** The persistence, progression, or recurrence of signs and symptoms of tuberculosis (fever, sweats, productive cough, documented weight loss, worsening of chest radiograph, progressive evidence of extra pulmonary tuberculosis) that is determined by the principal investigator (PI) to be due to tuberculosis and not due to another underlying cause.
3. **Clinical relapse:** Clinical or radiographic evidence of active tuberculosis after completion of therapy but before the end of the follow-up phase.

In addition to disease outcome status, participants will be categorized regarding completion of treatment status, defined as follows:

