 Indoor Air Pollution monitoring will be done only on a subset of cohort B households.

 Household food insecurity

 A complete physical exam at entry. At post-entry visits, a targeted physical exam will be performed

 For adults and children: Height / length, mid upper arm circumference, weight at baseline. At post entry visits, weight and height / length will be measured

 A 2 hour post TB drug dose (participant will take their dose in clinic and will have the time noted for a blood drawn 2 hours post dose administration)

 Additional EPTB samples to be collected at the discretion of the onsite clinical staff. These specimens are collected as part of clinical evaluation only and will not be retained/repeated for study purposes.

 CXR at baseline will be done unless one was taken as a part of the clinical investigation of the participant's TB through the RNTCP. Data from an 8 week and 6 month CXR will be collected if testing was done as part of the RNTCP standard of care or if participant has pulmonary disease. Pregnant women are not required to have CXR. CXR will be done at End of Tx if it didn't overlap with 6M

 CD4 count will only be performed on participants who have not had a CD4 count tested in the preceding 6 months.

 End of Treatment assessment of HbA1c will be selectively done on those participants with abnormal HbA1c at baseline

 Can be collected at any time-point between 2W and 6M

 At enrollment, one spot specimen and one early morning specimen will be obtained from all Cohort A participants. Diagnostic tests will be run on both specimens. During subsequent visits, two sputum spot specimens will be collected, and will be pooled for testing. The remaining specimens would be stored.

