## 9. STATISTICAL CONSIDERATIONS

### 9.1. SAMPLE SIZE AND ANALYSIS PLAN

**Aim 1.** The Active TB Cohort will include 800 adult PTB cases, 200 adult EPTB cases and 200 pediatric TB cases. The primary analysis set will be 800 adult PTB patients. Secondary analysis sets will include EPTB and pediatric TB.

Primary outcome is poor treatment outcome defined as failure, recurrence or death. Secondary outcomes will include time to AFB smear negativity, time to sputum culture negativity; time to detection of MGIT positivity. Host factors age, sex, DM, HIV, IAP exposure, tobacco exposure, malnutrition, and mental health will be key predictors for poor treatment outcomes.

Person-years of follow-up will be calculated for each member of the analysis set. Of TB patients who experience the outcome of interest, person-years of follow-up will be calculated as number of years between date of enrollment and date of event. Among those without the outcome person-years will be the number of years between enrollment and last date of follow-up. Crude treatment failure rates and 95% exact Poisson confidence intervals in the presence and absence of primary risk factors will be calculated. Adjusted treatment failure rate ratios will be estimated using multivariate Poisson regression models with person-years of follow-up as an offset. The Poisson regression models will also investigate interaction between individual and HH factors that might influence treatment outcomes.

A secondary subgroup analysis (may not be sufficiently powered) by enrollment sites, NIRT and BJMC, will be performed by adjusting the level of significance using a Bonferroni adjustment.

**Aim1 Power.** For Aim 1, we expect 20% (n=160) of 800 adult PTB cases will have the composite primary outcome (2% will fail, 6% will die, and 12% will have recurrence). This study will have at least 90% power at 5% level of significance to identify host and microbial risk factors (enumerated in section 3B3), with a prevalence of 10% - 40%, associated with poor treatment outcomes with relative risk ratio ranging from 1.5 to 6.0 over 24 months of follow-up.

**Aim 2.** The analysis set is individuals in the HH Contact Cohort: 3200 HH contacts of 800 PTB patients.

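### As section 8.1 is worded, an extrapulmonary or culture-negative paediatric patient whose disease progresses can be recorded as bacteriologically cured, with clinical failure closed

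*Protocol*

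**What the plan says.** Section 8.1 of the protocol sets one classification for all of Cohort A.

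- **Cure.** By the end of first-line therapy "the participant has two or more consecutive respiratory secretion cultures negative for" M. tuberculosis, "and no evidence of bacteriologic failure". There is no symptom, radiographic or disease-site element.
- **Indeterminate.** The participant "has resolution of symptoms of tuberculosis, but has not had two or more consecutive respiratory secretion cultures performed to establish cure status".
- **Bacteriologic failure.** By the end of therapy "the participant has one or more specimens from the respiratory tract or extra-pulmonary site that are culture-positive for" M. tuberculosis, false positives aside.
- **Order of use.** "Participants who do not meet bacteriologic criteria to establish their final status may be assigned a clinical outcome".
- **Clinical failure.** The listed signs include "worsening of chest radiograph, progressive evidence of extra pulmonary tuberculosis", judged by the principal investigator to be due to TB.

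Section 8 makes failure one part of the Aim 1 composite, with recurrence and death. Section 9.1 takes the 800 adult PTB patients as the primary analysis set and adds: "Secondary analysis sets will include EPTB and pediatric TB".

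**The concern.** Two negative sputum cultures show response only if the sputum was positive before. In disease that never reached the sputum they are negative whether or not treatment works. The cure definition does not make this distinction, and the order of use then sets aside the category written for such disease. A patient with enlarging nodes at month 6 and negative sputum throughout fits the description of clinical failure, yet meets the criteria for cure.

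What is at stake is the failure part of the composite in the EPTB and paediatric sets. Events that section 8.1 itself describes as failure can go uncounted. A comparison of poor outcomes between these sets and adult PTB would then partly reflect how the outcome is scored.

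**Working it through.** The protocol gives no figure to reproduce on this point. The check follows the 8.1 definitions as a decision rule and sets them against the specimen schedule.

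**Specimens available**

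- *Respiratory.* The first schedule-of-evaluations table in section 6.2 places sputum culture at entry, 2, 4 and 8 weeks, and 5 and 6 months, with no restriction to PTB. Footnote 13 takes the enrolment sputum from the whole cohort. Two negative cultures by the end of therapy are therefore attainable for an EPTB patient who can give sputum.
- *Extrapulmonary.* The same table marks a sample at entry and at the recurrence visit, whose column heading covers failure and relapse. Footnote 8, attached to the entry mark, says: "These specimens are collected as part of clinical evaluation only and will not be retained/repeated for study purposes". Section 6.3 leaves further extrapulmonary work to clinical indication. No routine on-treatment sample is scheduled at the diseased site.
- *Children under 5.* Section 6.3 specifies gastric aspirates. Section 8.1 does not say whether these count as respiratory secretions.

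**Four cases under 8.1**

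| Case | Two negative respiratory cultures | Positive culture elsewhere | Result |
|---|---|---|---|
| a. EPTB adult, never sputum-positive, disease progressing | yes | no | Cure; clinical failure closed |
| b. As a, with a positive extrapulmonary culture by end of therapy | yes | yes | Bacteriologic failure |
| c. Older child, culture-negative intrathoracic disease, radiograph worsening | yes | no | Cure; clinical failure closed |
| d. EPTB adult or young child, symptoms persisting | no | no | Neither cure nor indeterminate; clinical failure open |

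Cases a and c give the wrong result. Cases b and d do not. The indeterminate category does not rescue a or c, because it needs both resolved symptoms and missing cultures.

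**How many are exposed**

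EPTB adults plus children: 200 + 200 = 400. Share of Cohort A: 400 / 1200 = 33%. This is a ceiling on exposure, not a count of misclassified patients. Misclassification also needs progressing disease, two negative respiratory cultures and no positive culture elsewhere, and the protocol gives none of these proportions. Its one failure figure, 2%, is stated for adult PTB in section 9.1 and defined by smear positivity at 5 months in section 2.2, so it does not carry over to extrapulmonary disease.

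**Direction of bias**

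Let p1 and p0 be the true failure risks with and without a host factor, and s1 and s0 the shares of true failures that the rule detects. With no false failures, the observed ratio is (s1 × p1) / (s0 × p0). If s1 = s0 it reduces to p1 / p0: events and precision are lost, but the failure ratio is not shifted. If s1 and s0 differ, for example because the factor affects who can produce sputum, the ratio is multiplied by s1 / s0, which may lie above or below 1. In the composite, deaths and culture-positive recurrences still count, so the net direction also depends on how the factor relates to those parts.

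**The case against.** The strongest reply is that 8.1 has safeguards and is worded permissively. A positive culture from the diseased site defeats cure. Progressing nodes are just what would prompt such a sample, and the schedule marks one at the failure or relapse visit. The clinical-outcome sentence says who may receive a clinical outcome and does not say that no one else can. The recurrence definition names clinical failure alongside bacteriologic failure. Read strictly, the ordering would also bar a culture-cured patient from ever being a clinical relapse, which is unlikely to be intended.

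Much of this stands. Cure does not rest on sputum alone, and the strict ordering is the natural reading but not the only one. Two things remain. The safeguard works only through a positive culture: histology, imaging or visible progression without one changes nothing. And nothing in 8.1 lets clinical failure displace a cure already met, so at best two assessors could classify the same patient differently.

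A reader might also infer more than the protocol supports:

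- *That all sputum-negative EPTB patients and children with progressing disease are recorded as cured.* Cases b and d show otherwise. Section 5.2 also expects PTB, without an adult limit, to be positive by smear or Xpert at entry or confirmed by culture within 12 weeks, so fewer than all the children are likely to be exposed.
- *That the primary analysis is compromised.* It is restricted to adult PTB, and footnote 1 of the schedule removes participants still culture-negative at 3 months. At the edge, a confirmed adult who converts but worsens clinically meets the same ordering; that is a separate choice about the primary endpoint.
- *That associations are pulled towards the null.* The ratio above shows that this does not follow without further assumptions.

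**Conclusion.** The point holds in limited form. For an EPTB adult or a culture-negative child with two negative respiratory cultures, progressing disease and no positive extrapulmonary culture, 8.1 as written gives cure and closes the clinical category that describes the patient. The consequence is lost failure events in two secondary analysis sets. At most 400 of 1200 participants are exposed; how many would be misclassified cannot be derived from the protocol, and neither can the direction of any bias.

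This rests on two readings. First, meeting cure counts as having final status established bacteriologically. Second, the positive culture that defines failure is one that reflects response to treatment, not the diagnostic culture at entry. The point merits correction because it is a stated rule giving a wrong result, not a detail left for later.

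**What to change.** Amend 8.1 along these lines:

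- For EPTB participants and children, drug-susceptible bacteriologic cure applies only if a respiratory culture was positive at entry.
- Those without one are classified by the existing clinical outcomes: response, failure or relapse.
- A true-positive culture from any site still counts as bacteriologic failure or recurrence.
- The rule for the adult PTB primary set is unchanged.

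The same edit could say whether gastric aspirates count as respiratory secretions.

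The cost is small. Baseline cultures are already taken, and clinical assessment is scheduled at every Cohort A visit, so no procedure is added. Chest radiographs are scheduled at fewer visits and with conditions, so radiographic worsening will be judged on what is available. The downside is that more outcomes in the secondary sets will rest on investigator judgement.

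A general rule that clinical failure or relapse overrides cure is not proposed. It would also cover the EPTB patient or child who had a positive respiratory culture at entry, converts and then progresses elsewhere, which the narrower wording leaves as it is. But it would bring an investigator-judged override into the primary endpoint of the 800 adult PTB patients.
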